5. STUDY PROCEDURES

5.1 Schedule of Evaluations

Procedure	Baseline	3 months	6 months	9 months	12 months
Informed Consent	X				
Randomization	X				
Baseline clinical/demographic/lab info/baseline survey	X				
Immunosuppression levels and laboratory values collected from medical record	X	X	X	X	X
Interval health information collected		X	X	X	X
Patient-reported outcomes*	X	X			X
Phone Interview					X

*these include ITAS, PedsQL <18 years at enrollment or SF-36 if >18 years at enrollment, Reikert self-efficacy scale, PSSUQ (treatment arm only and only at 3 months)

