Participants will be enrolled in the study for 12 months. All subjects will complete study assessments and have immunosuppressant levels and clinical outcomes followed for 12 months. Subjects randomized to the intervention group will use the app for the first 3 months following enrollment. Subjects randomized to the control group will not use the app and will follow routine standard of care.

No study visits are required of research participants after enrollment, but they will complete surveys and an interview over the phone.

Procedure	Baseline	3 months	6 months	9 months	12 months
Baseline clinical/demographic/lab info/baseline survey	X				
Immunosuppression levels and laboratory values collected from medical record	X	X	X	X	X
Interval health information collected		X	X	X	X
Patient-reported outcomes*	X	X			X
Phone Interview					X

*these include ITAS, PedsQL <18 years at enrollment or SF-36 if >18 years at enrollment, Reikert self-efficacy scale, PSSUQ (treatment arm only and only at 3 months)

Sample Size and Population:

Participant enrollment will continue until we have reached 25 participants in each arm by age (13-21 years and 22 years and older) for a total of 100 participants. We will follow all study participants for 12 months.

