1.2 Secondary Objectives

- Clinical endpoints including rejection and hospitalization
- Patient reported adherence on immunosuppressant therapy instrument (ITAS)
- Patient-reported QoL outcomes as measured by PedsQL and SF-36
- Patient-reported self-efficacy using the Riekert Self-efficacy scale
- Patient-reported usability using the PSSUQ (treatment arm only)
- To examine the patterns of medication adherence in transplant recipients in both groups to better understand baseline medication adherence
- To understand the feasibility and acceptability of implementing such a system into the clinical workflow and patient follow-up care management

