8. INTERVENTION DISCONTINUATION

Participants may withdraw from the study at any time without penalty. This would not preclude participants from obtaining regular medical care or follow-up care related to their transplant. If participants choose to withdraw, the study team will use the data collected prior to withdrawal and mark the remaining data as censored.

Upon study completion or if study participation ends prematurely, those who were randomized to mDOT app will return to their usual standard of care. Those who were randomized to standard of care will continue in that manner.

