9. STATISTICAL CONSIDERATIONS

Primary outcome variables:

12-week immunosuppression medication adherence:

We will measure medication adherence in both arms at 12 weeks. The Medication Level Variability Index (MLVI) will be used to analyze immunosuppression lab

values to determine adherence with a relative risk noted for standard deviation >2 .

Secondary outcome variables:

- Hospitalization days
- Biopsy-proven rejection
- Clinician-assigned rejection

We will recruit 100 liver and kidney transplant recipients (50/arm), and compare recipients who received the mHealth intervention to controls that did not receive it. The Medication Level Variability Index (MLVI) will be used to analyze immunosuppression lab values to determine adherence with a relative risk noted for standard deviation >2 . Descriptive statistics will be performed to compare frequencies of secondary outcomes (e.g., hospitalization, rejection, etc). Patient reported outcomes will be scored as appropriate and differences compared between treatment arms. Additionally, we will perform subgroup analyses for younger transplant recipients (age at transplant <40), older transplant recipients, men, and women.

In addition to understanding the efficacy of this technology in a transplant patient population, we will also evaluate the feasibility of implementing such a system into clinical workflow. We will examine time spent by reviewers each week using mDOT, most ideal time post-transplant to consent and educate participants on using the application, and streamlining the workflow involved in the application. In order to ensure acceptability among the patients who will be using the app, we will survey all participants in the intervention arm at the end of the study period on their overall satisfaction in using the app. This survey will be administered with the ITAS scale over the phone. In addition, we will also examine consent rate and use of the mDOT app by participants over time to understand acceptability of using the application.

Feasibility will also be measured through phone interviews with all study participants at 12 months. We will contact all patients who consented to be in the study to participate in the phone interviews. The interviews will be semi-structured, with a set of pre-written questions as the guide. All interviews will be audio recorded. Transcription of the interviews will be conducted by Production Transcripts, Inc.

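### Censoring at study withdrawal, with no exit usability rating, makes the app-use summary describe those who stay and overstate continued use among the 50 randomised to the app

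*Combined protocol and SAP*

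**What the plan says.** Section 1.2 lists usability as a secondary objective ("Patient-reported usability using the PSSUQ (treatment arm only") and, as a separate item, feasibility and acceptability.

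The opening summary, under Interventions and Duration, sets the exposure period: "Subjects randomized to the intervention group will use the app for the first 3 months following enrollment". The footnote to the section 5.1 schedule fixes the usability rating at the end of that period: "PSSUQ (treatment arm only and only at 3 months". The same footnote stands under the schedule in the opening summary.

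Section 9 describes how acceptability will be judged. One element is a survey: "we will survey all participants in the intervention arm at the end of the study period on their overall satisfaction in using the app". Two more come in one sentence: "we will also examine consent rate and use of the mDOT app by participants over time to understand acceptability of using the application". Section 9 also plans 12-month interviews, under feasibility: "We will contact all patients who consented to be in the study to participate in the phone interviews". It gives no metric or denominator for app use and no rule for people who stop.

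Section 8 gives the only rule for people who leave the study: "the study team will use the data collected prior to withdrawal and mark the remaining data as censored". It adds that app-arm participants whose participation ends early go back to usual care. The documents plan no exit rating, no recording of reasons for leaving, and no counting of withdrawal as an acceptability outcome.

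**The concern.** Censoring suits a quantity that continues after a participant leaves but can no longer be seen. App use does not continue. Once a participant has left the study and returned to usual care, use is known to be zero. Marking it as censored turns a known zero into a missing value and removes that person from the later part of the app-use curve.

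For a question about acceptability this matters, because leaving may itself be the answer. Someone who withdraws in the third week because filming every dose is a burden is the person the trial most needs to count. Under section 8 as written, that participant contributes nothing to app use from week 4 on and never reaches the 3-month usability rating. Reported weekly use could stay flat and high while the share of the randomised group still using the app falls. A clinic deciding whether to offer the app needs the figure for everyone offered it.

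**Working it through.** **Plan's own figure.** 25 per arm in each of two age groups, two arms: 25 × 2 × 2 = 100, so 25 × 2 = 50 in the app arm. This agrees with section 9. The plan states no withdrawal rate and no target for app use or acceptability.

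**What happens to a participant who withdraws from the study at the end of week 3**
- App use, weeks 1 to 3: kept (section 8).
- App use, weeks 4 to 12: censored (section 8), although it is zero by the same section.
- Usability rating at 3 months: not obtained (section 5.1).

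**What happens to a participant who stops filming at week 3 but stays enrolled**
- Section 8 does not censor this person. Non-use is observable, and the 3-month rating is still due.

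The gap therefore concerns study withdrawal before month 3 only.

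**Week-12 use.** Assumed: stayers submit a share u = 0.90 of videos; a share p of the 50 has withdrawn by week 12; withdrawals are spread evenly over the 12 weeks.
- Among those remaining: u = 90%, whatever p is.
- Over all randomised: u × (1 − p).
  - p = 0.10 (5 of 50): 0.90 × 0.90 = 81%, an overstatement of 9 points.
  - p = 0.20 (10 of 50): 0.90 × 0.80 = 72%, an overstatement of 18 points.
- 12-week average over all randomised: u × (1 − p/2) = 85.5% for p = 0.10 and 81% for p = 0.20.

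**Check with leavers using the app less before they go.** Assumed: stayers use the app on 85% of 90 days; leavers use it on 50% of days and leave at day 30.

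| Withdrawn | Censored: use per day at risk | All randomised, zero after leaving | Month 3, those remaining | Month 3, all randomised |
|---|---|---|---|---|
| 5 of 50 | (45×90×0.85 + 5×30×0.5) / (45×90 + 5×30) = 3517.5/4200 = 83.8% | 3517.5/4500 = 78.2% | 85% | 45×0.85/50 = 76.5% |
| 10 of 50 | (40×90×0.85 + 10×30×0.5) / (40×90 + 10×30) = 3210/3900 = 82.3% | 3210/4500 = 71.3% | 85% | 40×0.85/50 = 68% |

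With 10 withdrawn, the overstatement is 11 points over the whole period and 17 points in month 3. It is smaller over the whole period because leavers' early use is kept.

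**Usability mean.** If leavers would score d points worse than stayers, the mean over all randomised differs from the stayers' mean by p × d: 0.1d or 0.2d for p = 0.10 or 0.20. The documents give neither d nor the scale. If d = 0, there is no bias.

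**The case against.** A reader might infer that people who dislike the app vanish from every acceptability measure, so that the trial is bound to make the app look better accepted than it is. The documents do not support that, for these reasons.

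- **Other measures exist.** Section 9 also names a satisfaction survey, the consent rate and 12-month interviews, and section 1.2 lists the PSSUQ as usability, separately from acceptability. Consent rate is settled before anyone can withdraw. The survey comes at the end of the study period and may share the gap. The interviews are worded to include everyone who consented, but the text does not say whether withdrawn participants are approached.
- **Leavers are not erased.** Their use before withdrawal stays in, including any decline before they leave.
- **Stopping the app is not leaving the study.** There are no study visits after enrolment, and payment follows completion, so some who dislike filming may simply stop and stay enrolled. They are not censored.
- **The denominator is not written down.** Section 9 never says that app use is computed among those still enrolled.
- **A zero is not always a verdict on the app.** Someone who leaves through illness or relocation has zero use for unrelated reasons, and counting them understates acceptability.

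The first three limit the point to early study withdrawal. The fourth is fair, but section 8 is the only rule given and makes no exception for app use, so following it produces the summary of those remaining. The last calls for a sensitivity summary. It does not justify censoring, because the share of the randomised group still using the app is a factual quantity whatever the reason for leaving. The single 3-month rating is not a fault in itself, since it falls at the end of planned use. What is missing is a rating at exit.

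**Conclusion.** The concern holds in limited form. For participants who withdraw from the study before month 3, section 8 treats known non-use as missing, and no usability rating is obtained. The summary of "use of the mDOT app by participants over time to understand acceptability of using the application" would then overstate continued use among the 50 randomised. That direction needs no assumption about why people left: if anyone withdraws and stayers still use the app, use among those remaining in later weeks exceeds use over all randomised.

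The size does rest on assumptions. With stayers submitting 90% of videos and 10% or 20% withdrawing, the week-12 figure is 90% against 81% or 72%. Neither input comes from the documents, and with no withdrawals the gap is zero. Bias in the usability mean is conditional: it is in the app's favour only if leavers would have rated the app worse.

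This bears on a secondary objective that has no stated threshold or test. The primary MLVI comparison is not affected. The change is still worth making, because the plan as written cannot report continued use for everyone offered the app.

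**What to change.** **Section 9, app use.** Define it as accepted videos divided by doses due, week by week to week 12, over all participants randomised to the app. Count weeks after stopping the app or withdrawing as zero use, and leave out weeks after death. Computing each participant's weekly proportion and then averaging over participants lets a leaver enter as zero without a count of doses due after they have gone.

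**Section 8.** State that this is an exception to the censoring rule.

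**Withdrawals.** Report the number withdrawing in the app arm, with reasons where participants offer them. Add a sensitivity summary that excludes withdrawals clearly unrelated to the app.

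**Usability rating (footnotes in the opening summary and section 5.1).** Keep the PSSUQ at 3 months for everyone still enrolled, including those who have stopped the app. Offer it at the last contact, as a voluntary request, to those who leave the study earlier. Report these exit ratings separately as well as pooled, because they follow a shorter exposure.

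**Survey and interviews.** Say whether withdrawn participants will be approached.

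The cost is protocol and SAP wording, a few short calls, and acceptability figures that will look somewhat less favourable.

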5.2 Description of Evaluations

5.2.1 Enrollment, Baseline, and Randomization

Consenting Procedure:

For all subjects:

When feasible to conduct in-person consenting, written consent will be obtained explaining the purpose of the study, their part in it, and that they can withdraw from the study at any time. As much time as necessary will be allowed for obtaining consent. Assent will be obtained from participants age 13-17 years, along with parental consent.

Additionally, we will make provisions for phone consent and enrollment if needed due to potential COVID-19 restrictions so that enrollment may proceed according to plan. If unable to conduct in-person consenting and enrollment process, patients will be contacted by phone and the study team will conduct the appropriate oral consent/assent procedures and conduct the procedures listed below remotely.

Enrollment and Baseline Assessments:

Once consent and, when applicable, assent is obtained, participants will complete a baseline survey containing questions about basic demographic, health, and smartphone usage information. After completing the baseline survey, subjects will be randomized into either the control or intervention arm. Study personnel will assist participants assigned to the mHealth intervention (mDOT) with downloading the mDOT application and explain its functioning. Patients will be strongly discouraged from discussing which treatment they are receiving with their clinical team.

In regard to using the mDOT app, a designated study team member will enter the medications prescribed and times to take the medications into the app for each participant in the intervention arm. As a second check, another member of the study team will ensure that medications entered into the app are consistent with what is in the patient's EHR to reduce the risk of transcription error. The app will then remind participants when it is time to take their medication, and what to take. Participants will then take a video of themselves taking the prescribed immunosuppression medications. A designated study team member will then review the uploaded videos and either accept or reject them in regard to adherence. Participants can view their progress, adherence, and what days they are expected to take their medications in a calendar-like view.

Randomization:

We will use block randomization to assign participants to the intervention or the control group using random block sizes ranging from 2 to 8. Block randomization will improve the probability of balanced groups over the course of the study as well as during shorter time horizons. A research data analyst, blind to the group allocations, will generate a list of sequential group assignments using this method. The list will be used to create sequentially numbered, sealed envelopes that will be used to allocate consenting participants to the control or intervention arms of our study. Each patient will have a 50% chance to be in the intervention arm of the study.

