4. SELECTION AND ENROLLMENT OF PARTICIPANTS

4.1 Inclusion Criteria

Participants must meet all of the following inclusion criteria to participate in this study:

- ≥ 13 years old
- Own a smartphone and are willing to receive information through it
- Received a liver or kidney transplant at a participating study site during or prior to the study period.

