4.2 Exclusion Criteria

All candidates meeting any of the following exclusion criteria at baseline will be excluded from study participation:

- Patients with cognitive impairments will not be eligible for enrollment due to inability to provide informed consent.
- Inability or unwillingness of individual or legal guardian/representative to give consent.

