4.3 Study Enrollment Procedures

Participants will be approached by the following methods:

For subjects ages 13-21 years old: either while they are an inpatient post-transplant or at any follow-up outpatient clinic visit by a study member to participate in this study.

For subjects >21 years old: either while they are an inpatient post-transplant or at their first post-op outpatient clinic visit by a study team member to participate in this study.

For all subjects:

When feasible to conduct in-person consenting, written consent will be obtained explaining the purpose of the study, their part in it, and that they can withdraw from the study at any time. As much time as necessary will be allowed for obtaining consent. Assent will be obtained from participants age 13-17 years, along with parental consent.

Additionally, we will make provisions for phone consent and enrollment if needed due to potential COVID-19 restrictions so that enrollment may proceed according to plan. If unable to conduct in-person consenting and enrollment process, patients will be contacted by phone and the study team will conduct the appropriate oral consent/assent procedures and conduct the procedures listed below remotely.

We will use block randomization to assign participants to the intervention or the control group using random block sizes ranging from 2 to 8. Block randomization will improve the probability of balanced groups over the course of the study as well as during shorter time horizons. A research data analyst, blind to the group allocations, will generate a list of sequential group assignments using this method. The list will be used to create sequentially numbered, sealed envelopes that will be used to allocate consenting participants to the control or intervention arms of our study. Each patient will have a 50% chance to be in the intervention arm of the study.

Participant enrollment will continue until we have reached 25 participants in each arm by age (13-21 years and 22 years and older) for a total of 100 participants and we will follow study participants for 12 months. No study visits are required of research participants after enrollment, but they will complete surveys and an interview over the phone.

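### The smartphone criterion does not ensure that a phone can run the app, and installation is first tried after randomisation, so some participants could be allocated to an intervention they cannot receive.

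*Combined protocol and SAP*

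**What the plan says.** Section 4.1 has one criterion about the device: "Own a smartphone and are willing to receive information through it". It names no operating system, camera, storage or data connection. Neither exclusion in section 4.2 concerns the phone; one is cognitive impairment and the other is "Inability or unwillingness of individual or legal guardian/representative to give consent".

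Section 5.2.1 sets the order of events. After consent, "participants will complete a baseline survey containing questions about basic demographic, health, and smartphone usage information". Then "After completing the baseline survey, subjects will be randomized into either the control or intervention arm". Only after that, and only in the app arm, "Study personnel will assist participants assigned to the mHealth intervention (mDOT) with downloading the mDOT application and explain its functioning". Use of the app means that "Participants will then take a video of themselves taking the prescribed immunosuppression medications", and a study team member reviews what is uploaded.

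No section describes a compatibility check, a trial installation or a rule for a failed installation. Section 8 covers withdrawal but not a participant who never starts the app. Section 9 names no analysis set.

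**The concern.** Being able to receive information on a phone is a weaker condition than being able to install a particular app, film doses and send the films. A candidate can meet the criterion and still hold a phone that cannot deliver the intervention, and the plan would find this out only once the arm is known.

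Two harms could follow, depending on how such a participant is analysed. Kept in the app arm, they contribute roughly the control risk to it and shrink the observed difference. Removed, replaced or moved to the control group, they break the randomised comparison, because a failed installation can be seen in one arm only. Control participants with equally unsuitable phones would never be identified and would stay in. Section 9 does not say which route would be taken.

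**Working it through.** **Plan's own figures.** The sample size agrees with itself. Section 4.3 asks for "25 participants in each arm by age (13-21 years and 22 years and older) for a total of 100 participants", and 25 × 2 arms × 2 age groups = 100, or 50 per arm as in section 9. The plan states no significance level, power, effect size or event rate, so there is no power figure to reproduce.

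**Inputs for an illustration**

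- n = 50 per arm (section 9).
- Two-sided significance level 0.05: assumed.
- Relative risk 0.50 for an MLVI above 2 among those able to use the app: assumed.
- Control risk pc: assumed. Section 2 reports non-adherence of 15–40% in adults and 50–70% in adolescents. The midpoints are 27.5% and 60%. Their mean, (27.5 + 60)/2 = 43.75%, reflects the equal age-group targets. These are general non-adherence rates used as a proxy; the documents give no rate for an MLVI above 2 at 12 weeks.
- q, the share of the app arm whose phone cannot run the app: assumed at 2–15%. With 50 in the arm, 2% is 1 participant, 5% is 2.5, 10% is 5 and 15% is 7.5.

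**Dilution if analysed as randomised.** Participants without a working app are given the control risk:

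- observed relative risk = q + (1 − q) × 0.50
- app-arm risk pt = pc × observed relative risk

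**Power.** With d = pc − pt and p̄ = (pc + pt)/2:

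- SE0 = √[2 p̄(1 − p̄)/50]
- SE1 = √{[pc(1 − pc) + pt(1 − pt)]/50}
- power = Φ[(d − 1.96 × SE0)/SE1]

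Worked case, pc = 0.4375 and q = 0.10:

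- observed relative risk = 0.10 + 0.90 × 0.50 = 0.55
- pt = 0.4375 × 0.55 = 0.2406, so d = 0.1969
- SE0 = 0.0947 and SE1 = 0.0926
- (0.1969 − 1.96 × 0.0947)/0.0926 ≈ 0.12, which gives power of about 55%

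| q | Observed relative risk | Power, pc 27.5% | Power, pc 43.75% | Power, pc 60% |
|---|---|---|---|---|
| 0 | 0.500 | 40% | 65% | 87% |
| 2% | 0.510 | 38% | 63% | 85% |
| 5% | 0.525 | 36% | 60% | 83% |
| 10% | 0.550 | 32% | 55% | 78% |
| 15% | 0.575 | 29% | 50% | 73% |

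The loss is about 1.5 to 2 points at 2%, and about 10 to 15 points at 15%.

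**Bias if dropped or moved.** No figure is given. The size depends on how far people with unsuitable phones differ in adherence from the rest, and the documents say nothing about that.

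**The case against.** The strongest reply is that nothing shows a real problem. The documents do not list the app's technical requirements, name an incompatible phone or give a failure rate. The criterion also asks for more than ownership. Smartphone use is surveyed before allocation, staff help with the download, and remote enrolment is a contingency for COVID-19 restrictions. Feasibility is a stated objective and section 9 plans to examine app use over time, so broad eligibility can be defended as giving a realistic estimate.

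Much of this stands. A reader might infer that people with unsuitable phones will in fact be randomised and will dilute the primary result. The documents support only that this could happen. Dilution also presupposes analysis by assigned arm, which section 9 does not state. Nor does the objective in section 1.1 settle the opposite. It speaks of those using the app and those who did not, but labels the two groups as intervention and control.

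A reader might also want to screen out people unwilling to film their doses. That goes too far. Consent comes before randomisation and explains the participant's part, so such people can decline. Those who enrol and then do not film still had the app available to them. Their non-use is part of the effect of offering it, and section 9 plans to study that as acceptability.

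What the reply does not answer is the sequence. The smartphone survey is tied to no eligibility decision, and help with a download cannot make an unsuitable phone suitable.

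**Conclusion.** The point holds as a modest gap in the design. Eligibility does not secure the technical means to receive the intervention, and the first test of those means comes after allocation, in one arm only.

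Its size cannot be established from the documents. Under the central assumptions, power goes from about 65% to between 63% (2% failures) and 50% (15% failures). If failures are rare, the gain from a check is small. Even with no failures, power in that scenario is only about 65%, so phone compatibility is not the main limit on what the trial can detect. The failure rate, relative risk, significance level and control risk are all assumptions, and the power figures apply only to an analysis by assigned arm.

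**What to change.** 1. Amend the smartphone criterion in section 4.1 to require a phone that meets the app's stated technical requirements (operating system, camera, storage and data connection).
2. Check this for every candidate during the baseline smartphone survey, in person or by phone, before the envelope is opened, so that it applies equally to both future arms.
3. Record failures in the REDCap screening log described in section 10.2.3 and report their number as a feasibility result.
4. Do not add a criterion on willingness to film.
5. State in section 9 that all randomised participants are analysed in their assigned arm. The check removes one cause of non-use; people who install the app and stop, or never begin, will remain.

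The cost is one amended criterion, a few added survey questions and a sentence in section 9. The downside is a slightly narrower sample, which reporting the excluded share makes visible.

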3. STUDY DESIGN

The purpose of this study is to understand how the use of an mHealth application, mDOT, changes medication adherence behaviors among liver or kidney transplant recipients. For the purpose of this research, the mobile app is a device of non-significant risk and exempt from the IDE requirement. emocha Mobile Health is the device manufacturer.

In this multi-center study, patients ≥ 13 years of age who receive a liver or kidney transplant at Johns Hopkins Hospital, University of Virginia Medical Center or University of Miami Medical Center will be recruited to participate in this randomized control trial (RCT). There will be 2 arms participants may be randomly assigned to: intervention and control arms. Participants in the intervention arm will receive the mDOT application, and participants in the control arm will not. Both arms will still receive standard of care post-transplant.

Participants are followed for their compliance with standard of care recommendations. No additional care or procedures will be administered to study participants. Given the uncertainty in whether this mHealth intervention will improve rates of immunosuppression medication adherence in liver and kidney transplant recipients, a non-treatment group is necessary in order to identify whether an advantage exists.

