10.2.3 Screening and Enrollment Tracking

Recruitment and retention at the sites will be supported by a centrally managed electronic data collection (EDC) system in REDCap where data will be entered on every screening and enrollment, including inclusion and exclusion criteria met, and demographics needed for reporting. Enrollment reports will be generated monthly and reported annually as part of the renewal process.

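### One unstratified randomization list serves three hospitals and an age quota, so chance imbalance by site and age is left uncontrolled in both design and analysis

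*Combined protocol and SAP*

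**What the plan says.** The same randomization paragraph appears in the synopsis, in Section 4.3 and in Section 5.2.1. Allocation is blocked, "using random block sizes ranging from 2 to 8". An analyst "will generate a list of sequential group assignments using this method", and then: "The list will be used to create sequentially numbered, sealed envelopes that will be used to allocate consenting participants". The ratio is 1:1 ("Each patient will have a 50% chance to be in the intervention arm of the study"), and the stated purpose of blocking is balance in time: "Block randomization will improve the probability of balanced groups over the course of the study as well as during shorter time horizons". Site, organ and age are not named as strata.

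Three enrolling hospitals are named in Section 3 ("transplant at Johns Hopkins Hospital, University of Virginia Medical Center or University of Miami Medical Center will be recruited"). The synopsis and Section 4.3 continue enrollment until there are 25 participants in each arm in each age group (13–21, and 22 and older), 100 in all. Section 9 gives 50 per arm, mentions no adjustment for site or for this age split, and lists subgroups by sex and by age at transplant below 40 only.

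The plan does not say who holds the envelopes, or whether each hospital has its own set. Section 10.2.1 creates a coordinating center but does not list allocation among its duties. Section 10.2.3 describes a "centrally managed electronic data collection (EDC) system in REDCap" for screening and enrollment data, not for allocation.

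**The concern.** A list blocked only in enrollment order balances the running total. It does not balance any subset of participants, such as one hospital or one age group. Two subsets matter here.

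- **Site.** The primary outcome is the standard deviation of drug levels taken from routine records (Sections 5.2.3 and 9), and Section 3 adds no study procedures. How often and how levels are drawn is therefore each hospital's own practice. If that practice affects the index, a chance excess of one arm at one hospital adds noise to the arm comparison, and no planned adjustment removes it.
- **Age.** The plan sets its own target of 25 per arm per age group, and the described list does not deliver it.

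**Working it through.** **Inputs.** From the plan: N = 100, 1:1 allocation, three sites, block sizes 2 to 8, age groups 13–21 and 22+. Assumed: even block sizes 2, 4, 6 and 8 with equal probability; site shares of 34/33/33, 50/25/25 and 60/20/20 (the plan gives none); 50 people per age group; site and age unrelated to position in the list.

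**The plan's own figure.** 25 × 2 arms × 2 age groups = 100, or 50 per arm. It reproduces. The plan gives no power calculation to check.

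**Analytic check, site.** If the list ends 50:50, the intervention count in a site of 34 is hypergeometric, with variance 34 × 0.25 × (66/99) = 5.67 and SD 2.38. The arm difference has SD 2 × 2.38 = 4.76 and mean absolute value of about 0.80 × 4.76 = 3.8. Simulation gives 3.8.

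**Analytic check, age.** For 50 of 100, P(exactly 25) = C(50,25)² / C(100,50) = 0.158. This is an upper limit, because the last block may be incomplete and the list may not end 50:50; simulation gives 0.117. The variance is 50 × 0.25 × (50/99) = 6.31, SD 2.51, so the 95% range is 25 ± 1.96 × 2.51, about 20 to 30. Simulation agrees.

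**One list in enrollment order (simulated, 10,000 to 20,000 trials per scenario).**

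| Site sizes | Any site differs by 8 or more | Any site 60:40 or worse | Any site 70:30 or worse |
|---|---|---|---|
| 34/33/33 | 24% | 38% | 1% |
| 50/25/25 | 23% | 57% | 4% |
| 60/20/20 | 24% | 70% | 15% |

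Repeat runs of the first column ranged from 22% to 25%. The 95th percentile of the overall arm difference is 2.

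**Separate lists by site and age group (six strata, same block sizes).** An incomplete block of 8 leaves a difference of at most 4 per stratum. The theoretical caps are therefore 2 × 4 = 8 per site and 3 × 4 = 12 per age group. Simulated results over the same three site mixes:

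- Worst-site difference: 95th percentile 3–4, never above 8.
- Worse age group: 95th percentile 4, maximum 8. A difference of 4 in a group of 50 is 27 v 23, two off 25 per cell; a difference of 8 is 29 v 21, four off.
- Overall difference: 95th percentile 6.
- Exactly 25/25 in both age groups: about 18%. Stratification narrows the miss more than it raises the chance of an exact hit.

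**What one imbalance does.** A site split 21 v 13, with 50 per arm, changes that site's weight in the contrast by 21/50 − 13/50 = 0.16. If that site's mean differs from the others by an assumed 0.5 SD, the contrast moves by 0.16 × 0.5 = 0.08 SD. The standard error with 50 per arm is √(2/50) = 0.20 SD.

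**The case against.** The strongest reply is that randomization without site strata is valid. This stands: the comparison is unbiased over repeated trials, and what is lost is precision. In the example above the shift is 0.08 SD against a standard error of 0.20 SD, and no site effect on the variability index is documented.

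A reader might infer that one envelope sequence cannot be followed at three hospitals. The documents do not support that. One central holder could open the envelopes in order for all sites, for example by phone. Alternatively, the series could be divided into consecutive runs per hospital. That leaves little imbalance: a 60:40 or worse split in any site in 0%, 1% and 6% of trials for the three site mixes. The plan is silent on custody, which is a gap but not an impossibility. The figures of 23–24% apply only if the list is used in enrollment order across sites.

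A reader might also infer that sites will be badly unbalanced. That depends on site sizes the plan does not give. With three equal sites, 70:30 or worse occurs in about 1% of trials; with an extreme 80/10/10 mix it occurs in about 53%.

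Finally, the plan describes REDCap for data capture and tracking only, so its use for allocation cannot be assumed. Numbered sealed envelopes with random block sizes already give some concealment.

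**Conclusion.** The point holds as a cheap improvement, not a flaw that invalidates the trial. As written, site and age group are controlled by neither the allocation nor the described analysis. Used in enrollment order, the list leaves some site 8 or more apart in about 23–24% of trials and misses an exact 25/25 split in both age groups in about 88%. The first figure depends on the assumed site shares, and the second on 50 participants per age group; both assume even block sizes. The harm depends on a site or age effect on the outcome, which is plausible because levels come from each hospital's routine care, but which the documents do not show. They do not support a claim of bias or of an unworkable sequence.

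**What to change.** In Section 5.2.1, and in the matching text of the synopsis and Section 4.3:

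1. Generate separate permuted-block lists for each site by age group (13–21 / 22+), six lists in all, with small block sizes.
2. State who holds and releases assignments. Central release after consent and the baseline survey is preferable, through REDCap if its randomization function is available. If envelopes stay, name the holder and say whether each site has its own set.
3. State how the quota of 25 per cell is applied when a cell fills early or ends short.

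In Section 9, include site and age group in the primary analysis of the Medication Level Variability Index. This takes three degrees of freedom: two for site and one for age.

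**Cost.** Setting up six lists instead of one. With the stated block sizes, incomplete final blocks raise the 95th percentile of the overall arm difference from 2 to about 6. A cell may typically be up to two off 25, and in simulation at most about four. In a check with blocks of 2 and 4 only, the overall 95th percentile was 4. Shorter blocks are easier to predict, however, and Section 5.2.2 leaves enrolling staff unmasked, so block sizes should be kept from them.
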